8.0 Study Calendar

Timeline	Birth	Admission to NICU	Treatment	Discharge	Follow-up
Study Procedures	Screening for potential eligibility based on opioid exposure	Determine eligibility and approach for enrollment	Follow treatment course	Final data collection on outcomes	Phone call/chart review) at 4-8 weeks of age to assess for re- admission
		Collect baseline maternal and newborn data	Monitor for protocol deviations, issues, AEs, SAEs	Confirm contact information for follow-up phone call	
		Randomize	Continue data collection		

9.0 Reportable Events

An adverse event (AE) is defined as any untoward medical occurrence in a subject in the investigation. AEs must be assessed for expectedness, severity, attribution (relatedness to the study intervention), and seriousness by the investigator, or another qualified study team member as characterized below. AEs deemed related to the intervention must be reported as serious adverse events (SAEs) if they become serious (become life-threatening, result in death, or prolong hospitalization). Recording of such adverse events will start at the time of the study consent and will stop upon discharge from the hospital.

The following criteria will be used to define relatedness:

Definite: The AE is clearly related to the study intervention

Probable: The AE is likely related to the study intervention

Possible: The AE may be related to the study intervention

Unrelated: The AE is clearly not related to the study intervention

The severity of AEs will be described as:

Mild: asymptomatic or mild symptoms, no intervention indicated

Moderate: clinically significant requiring minimal noninvasive intervention

Severe: severe or medically significant but not immediately life-threatening, need for intensive, emergent, or invasive intervention

Life-threatening: life-threatening physiological consequences, need for intensive or emergent invasive intervention

Newborns with NAS are at risk of several complications related to their withdrawal symptoms. They may experience excessive weight loss in the first 1-2 weeks of life (>10% of their birth weight), they may have oromotor dysfunction and require supplement gavage feedings to support growth, and in rare cases, they can have seizures. Adverse events will be monitored monthly by the study team and collected in REDCap. Infants who receive morphine are at risk of over-sedation and decreased level of consciousness, as well as respiratory depression that can result in apnea. While this risk is mitigated by the fact that infants with NAS are opioid-tolerant, it remains a risk especially when escalating the dose. Per standard care, all infants receiving morphine remain on cardiopulmonary monitoring throughout their treatment.

Adverse Event monitoring will include:

- 1. Depressed level of consciousness
 - Grade 1: Decreased level of alertness

Grade 2: Sedation; slow response to stimuli; sleeping longer than expected or needing to be aroused at feeding times

Grade 3: Difficult to arouse

Grade 4: Life-threatening consequences; coma; urgent intervention indicated Grade 5: Death

- 2. Other events classified as serious and unexpected
- 3. Other events resulting in death or classified as Serious or Related (to study procedures)

A depressed level of consciousness grades 1-3 will be considered an AE, while grade 4 will be considered a SAE. All SAEs and AEs reported during this study will be followed until resolution or until the investigator confirms that the AE/SAE has stabilized and no more follow-up is required. All deaths and SAEs that are at least possibly related and all unexpected SAEs will be

reported to the investigator within 24 hours of the study team becoming aware. An initial SAE form must be as complete as possible, including details of the current serious adverse event, including an investigator assessment of the causal relationship between the event and study procedures. Information not available at the time of the initial report must be documented on a follow-up SAE form. All unexpected SAEs will be reported to the IRB within 5 working days. The study team will begin tracking AEs and SAEs at the time of consent and will conclude tracking after the follow-up phone call has been made when the infant is 4-8 weeks of age.

We will not report deviations as clinical care is being followed. This is a pragmatic pilot trial that is not intended to alter the standard of care treatment. It is ideal that the morphine is dosed every 3 hours/FINN scores obtained for those on the standard arm. However, there will be times this does not occur, and it will not be considered a protocol deviation.

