5.0 Study Design

This will be a pragmatic pilot randomized controlled trial comparing scheduled versus intermittent morphine dosing for severe neonatal abstinence syndrome, performed in the Riley Hospital for Children Neonatal Intensive Care Unit (NICU) at IU Health Methodist Hospital. In 2018, 154 babies admitted to IU Health Methodist were exposed to opioids in utero. [name] has clinically treated and conducted research with this population since 2015. We hypothesize that treating NAS symptoms on an as-needed basis will result in decreased use of morphine and decreased length of stay. Severity of NAS will be defined by the modified Finnegan scoring tool, which is already in use.¹² This tool is administered by the bedside nurse

every 3-4 hours and uses graduated scoring of 21 items which are then added together to give the modified Finnegan score.

The current guideline for pharmacologic treatment of neonatal abstinence syndrome uses the modified Finnegan score to determine the severity of symptoms. Modified Finnegan scoring should be performed every 3 hours after a feeding. If an infant reaches the threshold score for treatment (\geq 9), morphine is initiated at 0.05 mg/kg/dose orally every 3 hours. If the modified Finnegan score continues to be elevated, the dose is escalated per a protocol until the modified Finnegan score is in an acceptable range. Once the infant's modified Finnegan score has been stable for at least 48 hours on a particular morphine dose, the weaning phase begins. Morphine is weaned by 10% of the peak dose every 24 hours as tolerated based on symptoms. When the dose has been weaned to < 0.02 mg/kg/dose, it may be discontinued. In order to be discharged home from the hospital, the infant needs to remain stable off of morphine for at least 48 hours. The study group will also be assessed using the modified Finnegan scoring tool. These infants will receive morphine at the same starting dose of 0.05 mg/kg/dose but on an asneeded basis as often as every 3 hours if the modified Finnegan score reaches the threshold for treatment. Our goal is to enroll 24 participants with 12 patients on each arm. A success rate would be a retention of 80% (approximately 20 participants).

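### Section 9.0 is inconsistent on whether relatedness is part of the SAE definition, and a non-fatal serious event judged expected and unrelated has no timed reporting route

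*Combined protocol and SAP*

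**What the plan says.** All of the definitions are in Section 9.0 of the combined protocol and SAP.

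- **Assessment.** "AEs must be assessed for expectedness, severity, attribution (relatedness to the study intervention), and seriousness by the investigator, or another qualified study team member". The relatedness scale runs from definite to unrelated, and its last category is strict: "Unrelated: The AE is clearly not related to the study intervention". The section gives criteria for relatedness and severity but none for expectedness.
- **General SAE rule.** "AEs deemed related to the intervention must be reported as serious adverse events (SAEs) if they become serious". The seriousness criteria that follow are that events "become life-threatening, result in death, or prolong hospitalization".
- **Specific SAE rule.** Of depressed level of consciousness, the section says "grades 1-3 will be considered an AE, while grade 4 will be considered a SAE". No attribution test is attached. Grade 5, which is death, is on the scale but not in this sentence.
- **24-hour report to the investigator.** It covers "All deaths and SAEs that are at least possibly related and all unexpected SAEs".
- **IRB report.** "All unexpected SAEs will be reported to the IRB within 5 working days".
- **Recording window.** The opening paragraph of Section 9.0 ends AE recording at hospital discharge. A later paragraph continues tracking of AEs and SAEs until after the follow-up call at 4-8 weeks of age.

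Section 10.0 adds that every AE and SAE is discussed at once, referring back to Section 9.0, and it places safety monitoring with the study team. Sections 8.0 and 15.0 describe the 4-8 week contact, whose stated purpose is to find readmissions.

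**The concern.** An SAE definition should let two people classify the same event in the same way. Here, someone who follows the general rule would leave a serious event judged unrelated off the SAE list. Someone who follows the later text would put it on. The reporting rules then do not cover one class of event under either approach.

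That class matters in this trial. Section 9.0 names seizures, excessive weight loss and need for gavage feeding as known complications of withdrawal. Because expectedness has no criteria, these are natural candidates for being called expected, and they are readily attributed to the syndrome. Yet the trial is "comparing scheduled versus intermittent morphine dosing for severe neonatal abstinence syndrome", so it changes how withdrawal is treated, and complications of under-treatment are a plausible harm of the as-needed arm. The pilot is meant to inform a larger trial. With 12 infants planned per arm, the classification of a single serious event would change an arm's safety summary.

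**Working it through.** No arithmetic beyond counting applies. The check sets the rules of Section 9.0 against each other and follows each type of serious event through them. Related here means possibly, probably or definitely related. The documents do not say which categories satisfy the general rule.

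**Step 1: is relatedness part of the definition?** The general rule says yes. Four places later in Section 9.0 point the other way:

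- The 24-hour rule singles out SAEs that are at least possibly related, which presupposes that others are not.
- The list of monitored events includes those classified as serious or related, as alternatives.
- Grade 4 depressed consciousness is an SAE whatever its cause.
- The SAE form asks for a causality assessment, so causality is judged on an event already called an SAE.

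**Step 2: which serious events reach a timed report?**

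| Serious event | SAE by the general rule, read literally? | SAE by the later usage? | 24-hour report | IRB report |
|---|---|---|---|---|
| Non-fatal, related, unexpected | Yes | Yes | Yes | Yes |
| Non-fatal, related, expected | Yes | Yes | Yes | No |
| Non-fatal, unrelated, unexpected | No | Yes | Literal: no. Later usage: yes | Literal: no. Later usage: yes |
| Non-fatal, unrelated, expected | No | Yes | No on both | No on both |
| Death, unrelated, expected | No | Yes | Yes if deaths are covered unconditionally, otherwise no | No |
| Grade 4 depressed consciousness, unrelated | No, but the grade 4 sentence makes it one | Yes | By the grade 4 sentence: yes if unexpected, no if expected | By the grade 4 sentence: yes if unexpected, no if expected |

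The first four rows are the four non-fatal combinations of relatedness and expectedness. One has no timed route on either reading. On the literal reading there are two.

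**Step 3: readmission.** The listed criteria are death, threat to life and prolonged hospitalization. An infant discharged and later readmitted meets none of them unless the event is fatal or life-threatening. The follow-up can therefore find the event it was designed to find without that event being serious under the protocol.

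**Step 4: recording window.** If recording stops at discharge, an event found at the follow-up call is outside the AE record altogether. If tracking runs to the call, it is inside. Section 9.0 says both.

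**The case against.** The strongest reply is that little is lost. Every AE is assessed for expectedness, severity, attribution and seriousness and is collected in REDCap, so a serious unrelated event stays in the data. Section 10.0 has any AE or SAE discussed immediately, with no filter. The unrelated category demands that the event clearly be unrelated, so a withdrawal seizure to which less morphine may have contributed belongs under possible; if serious, it then falls under the 24-hour rule, provided that possible counts as related. Apnea is listed as a risk of morphine and would ordinarily be at least possibly related. Weight loss and gavage feeding are not serious on the listed criteria unless they prolong the stay. Length of stay and readmission are collected in any case.

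Most of this stands, and it limits the point. It does not remove the contradiction or supply a timed route for the uncovered class. The Section 10.0 discussion refers back to Section 9.0 and states no deadline in hours or days and no recipient outside the team.

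A reader might infer three stronger things that the documents do not support:

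- **That SAEs are simply defined by relatedness.** The later text of Section 9.0 contradicts this, so the finding is inconsistency.
- **That unrelated expected events escape every rule.** The 24-hour rule most naturally covers all deaths unconditionally, and Section 10.0 adds the internal discussion.
- **That the safety comparison is biased by unblinded attribution.** Blinding is not mentioned. Open-label judgement is a fair inference from the two regimens but is not stated. No arm-level SAE analysis is specified, and no event frequency is given.

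**Conclusion.** The point holds as a defect in the stated rules. Section 9.0 contradicts itself on whether relatedness decides SAE status, and a non-fatal serious event judged expected and unrelated has no timed report on any reading. The omission of readmission and the two end points for AE recording add to it.

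The effect on results cannot be sized from the documents. Under-counting of under-treatment harms in the as-needed arm is a plausible risk, not a shown one. It assumes that named complications of withdrawal would be called expected and that some would be judged clearly unrelated. The contradiction and the reporting gap depend on neither assumption. The sponsor should correct the text because the correction is nearly free and bears on safety reporting in newborns.

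**What to change.** Amend Section 9.0 as follows.

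1. Define an SAE by seriousness alone: an AE that results in death, is life-threatening, prolongs hospitalization or leads to readmission.
2. Keep relatedness and expectedness as the separate assessments they already are, and state that neither decides SAE status.
3. Bring serious events judged expected and unrelated under the 24-hour report to the investigator, so that the rule covers every SAE. This also removes the doubt about whether deaths are covered unconditionally.
4. Make the depressed-consciousness sentence agree with the definition and place grade 5 in it.
5. Give one end point for AE and SAE recording. If readmission is a seriousness criterion, the window has to reach the 4-8 week contact.
6. State that SAEs will be tabulated by arm regardless of attribution.

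The cost is protocol wording and possibly a few more SAE forms. No new study procedure is needed.

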15.0 Follow-up and Record Retention

The duration of the study will from be from enrollment through 4-8 weeks of age. The majority of the data collection and monitoring will be done during the initial hospital stay. Once the infant is discharged from the NICU, we plan to contact the parent via phone for follow-up to determine if the infant has required readmission to the hospital for any issues potentially related to neonatal abstinence syndrome in the first month of life. If the baby stays in the IU Hospital system after birth, the study team will look for recent appointments that may contain the follow up information.

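### Section 9.0 ends adverse-event collection at hospital discharge in one place and after the 4–8 week follow-up call in another

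*Combined protocol and SAP*

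**What the plan says.** The early part of Section 9.0 (Reportable Events), after defining adverse events and how they are assessed, states: "Recording of such adverse events will start at the time of the study consent and will stop upon discharge from the hospital".

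Further on in the same section, after the SAE reporting rules, the study team is to begin tracking AEs and SAEs at consent and "will conclude tracking after the follow-up phone call has been made when the infant is 4-8 weeks of age". A separate sentence there deals with events already known: "All SAEs and AEs reported during this study will be followed until resolution", or until the investigator confirms that they have stabilized.

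Two other sections bear on the question:

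- Section 15.0 (Follow-up and Record Retention) says "The duration of the study will from be from enrollment through 4-8 weeks of age". The contact it describes is a call to the parent about readmission potentially related to NAS in the first month. For infants who stay in the hospital system, "the study team will look for recent appointments that may contain the follow up information".
- Section 8.0 (Study Calendar) has the entry "Monitor for protocol deviations, issues, AEs, SAEs", which appears to sit in the Treatment column. The Follow-up column has "Phone call/chart review) at 4-8 weeks of age to assess" for readmission and does not mention adverse events.

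**The concern.** The two statements share a start (consent) and differ in their end. A coordinator who follows the first closes the adverse-event record at discharge. One who follows the second keeps it open until the follow-up contact. Both would be complying with Section 9.0, and infants in the same trial could be handled differently.

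What is at stake is the completeness of the safety record after the infant goes home. Under the discharge rule, a new event at home is outside the recording period. Even a readmission learned of at the follow-up contact would count as follow-up information and not as an AE or SAE. The pilot exists to prepare a larger trial, so an unclear collection window may be carried forward with its procedures.

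**Working it through.** The main check is textual. A short calculation then sizes the disputed period.

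**1. The two statements side by side**

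| | Section 9.0, first statement | Section 9.0, later statement |
|---|---|---|
| Activity | recording | tracking |
| Events | the adverse events just described | AEs and SAEs |
| Start | consent | consent |
| End | hospital discharge | after the call at 4–8 weeks of age |

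**2. Readings that might remove the conflict**

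- *The first statement covers only a subset, namely related events that become serious.* The later statement covers all AEs and SAEs, so that subset still has two end dates.
- *Recording means capturing new events, and tracking means following known ones.* Following known events has its own sentence ("All SAEs and AEs reported during this study will be followed until resolution"). The tracking sentence also has its own start at consent, so it describes a full collection window.
- *AEs are collected to discharge and SAEs to the call.* The later statement names both, and nothing in the document assigns them different windows.

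None of the three works.

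**3. Whether other sections settle it**

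Section 15.0 supports the longer window. The calendar leans the other way, since AE/SAE monitoring appears under Treatment and only readmission under Follow-up. The table layout may have suffered in extraction, so little weight should rest on its columns. The conflict stands on Section 9.0 alone.

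**4. Size of the disputed period**

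Inputs:
- Follow-up contact at 4–8 weeks of age (Sections 8.0, 9.0 and 15.0): 4 × 7 = 28 days to 8 × 7 = 56 days.
- Mean length of stay of morphine-treated infants in 2018 (Section 1.0): 21.5 days. I assume this is counted from birth, as Section 3.0 does for the trial outcome, so that stay and age share one clock.

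Formula: disputed days = age at contact − age at discharge.

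- Contact at 4 weeks: 28 − 21.5 = 6.5 days.
- Contact at 8 weeks: 56 − 21.5 = 34.5 days.

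The period lengthens day for day with earlier discharge. As an illustration, take a stay shorter by the 5-day difference named in Section 12.0: 21.5 − 5 = 16.5 days. The period is then 28 − 16.5 = 11.5 days to 56 − 16.5 = 39.5 days.

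The protocol states no figure of its own for this period, so there is none to reproduce.

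**The case against.** The best defence is that the intended window can be worked out. The later statement is the more specific, it names both AEs and SAEs, and it agrees with the study duration in Section 15.0. Events open at discharge are followed to resolution in any case. The trial is a pilot of 24 infants whose primary outcomes concern enrollment, drop-out and switching to the standard arm.

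Much of this stands. It would be too strong to say that staff have no means of choosing, because the weight of the text favours the longer window. But the shorter one is stated outright and the calendar appears to follow it, so the text still permits both.

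A reader might also draw stronger conclusions that the documents do not support:

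- *Infants followed only by chart review have no end date.* The later statement in Section 9.0 does mention only a phone call. However, the calendar allows a call or chart review at 4–8 weeks, and Section 15.0 ends the study within that range. An outer limit of 8 weeks therefore exists, and only the wording needs aligning.
- *Required safety reports would be missed.* Section 9.0 says "All unexpected SAEs will be reported to the IRB within 5 working days" and sets a 24-hour report to the investigator. That 24-hour clock runs from the team becoming aware, and no post-discharge contact before 4–8 weeks is described. Missed reports are a conjecture. What follows from the text is that new post-discharge events would go unrecorded under the discharge rule.
- *The arms would be compared unfairly.* If as-needed dosing shortens stay, as Section 5.0 hypothesizes, a discharge cut-off would observe that arm for less time. But adverse events are not an outcome in Section 3.0 and no between-arm comparison of harms is planned, so no planned result is biased.

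**Conclusion.** The contradiction is real and confidence in it is high, because it rests on two current sentences of one section and on no assumption. Its size is 6.5 to 34.5 days of adverse-event collection for an infant discharged at the 2018 mean stay, and more for earlier discharge. That range assumes that the 2018 mean is counted from birth and is a fair guide to the trial infants. It describes an infant at the mean and is not an average over infants, whose stays will vary.

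The consequence is limited to the completeness and consistency of safety data after discharge. The feasibility outcomes, the length-of-stay and morphine outcomes, and the 12 per group are untouched. This should be corrected, but it does not threaten the trial.

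**What to change.** Reconcile Section 9.0 to one collection window and align the calendar. The simplest way uses an end point that the protocol already states:

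1. In the first statement of Section 9.0, replace the discharge cut-off with the end point of the later statement.
2. Word that end point identically in both places, as the planned follow-up contact, by phone call or chart review, at 4–8 weeks of age.
3. Add AE/SAE collection to the Follow-up column of the Section 8.0 calendar.

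If the sponsor intends different windows for AEs and SAEs, that would also remove the conflict, provided each window is stated explicitly in both parts of Section 9.0 and in the calendar.

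The cost is a change of wording and a few more questions at a contact already planned. There is no extra visit, and the study duration in Section 15.0 is unchanged. One weakness would remain: capture will be poorer for infants followed by chart review alone, because a chart shows only events seen within that hospital system.

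### Section 9.0 describes five harms but solicits and grades only depressed consciousness, so expected, non-serious withdrawal harms may be captured inconsistently

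*Combined protocol and SAP*

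**What the plan says.** Section 9.0 (Reportable Events) first gives a broad definition under which any unwanted medical event in a participant is an adverse event, to be assessed for expectedness, severity, relatedness and seriousness. It then describes the complications of withdrawal. One is weight loss above 10% of birth weight. Of the others it says that "they may have oromotor dysfunction and require supplement gavage feedings to support growth, and in rare cases, they can have seizures". It goes on to the risks of morphine: over-sedation with reduced consciousness, and respiratory depression leading to apnea.

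The list that follows opens with "Adverse Event monitoring will include" and has three items:

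1. "Depressed level of consciousness", graded 1 to 5, starting from a mere reduction in alertness.
2. "Other events classified as serious and unexpected".
3. "Other events resulting in death or classified as Serious or Related (to study procedures").

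Section 5.0 (Study Design) hypothesizes that as-needed treatment "will result in decreased use of morphine and decreased length of stay". Section 3.0 lists feasibility measures, length of stay and morphine exposure as outcomes, with no safety endpoint. Section 12.0 specifies no comparison of adverse events between arms.

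**The concern.** The section sets out harms in both directions, too little and too much morphine, and then asks staff to look for one of them by name. That one is a harm of more morphine, and it is recorded down to its mildest grade. The three withdrawal harms are not named. Because the section itself foresees them, they are unlikely to count as unexpected. Unless they are serious, they reach the list only if someone judges them related. No blinding is described, so that judgement is made by staff who know the arm.

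What is at stake is the descriptive adverse-event table. Section 12.0 says the pilot data are needed to design a larger trial, and Section 1.0 says many centers already want to adopt as-needed dosing without randomized evidence. If withdrawal harms were not looked for in the same way in every infant, a low count of them cannot be interpreted.

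**Working it through.** The plan states no adverse-event rate or safety calculation, so there is no figure to reproduce. The 108 per group in Section 12.0 concerns length of stay and has no bearing here. The check sets the harms in Section 9.0 against its own monitoring list.

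**Step 1. Harms against the list**

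| Harm described in 9.0 | Source | Named and graded? | Otherwise enters the list if |
|---|---|---|---|
| Weight loss >10% of birth weight | withdrawal | no | serious or related |
| Gavage feeding for oromotor dysfunction | withdrawal | no | serious or related |
| Seizures | withdrawal | no | serious or related |
| Over-sedation / reduced consciousness | morphine | yes | not applicable |
| Respiratory depression / apnea | morphine | no | serious or related |

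One of five harms is named: 1 of 2 from morphine and 0 of 3 from withdrawal. In 9.0, serious means life-threatening, fatal or prolonging the hospital stay. Item 3 therefore catches a life-threatening seizure, or gavage feeding that extends the stay, whether or not it was expected. The exposed group is the non-serious events.

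**Step 2. Do other data fill the gap?** Section 7.0 lists birth weight, Finnegan scores and nutrition as breast milk or formula. It does not list later weights, gavage feeding or seizures. The scoring form in Appendix 1.0 has a convulsions item, a poor-feeding item and a daily-weight entry, but the plan does not say that item-level scores or the weights are captured.

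**Step 3. Direction and possible size.** All rates here are assumptions chosen so that the true totals tie. Take 12 infants per arm (Section 5.0), sedation in 30% scheduled and 10% as-needed, and a non-serious withdrawal harm in 10% scheduled and 30% as-needed. Let c be the fraction of withdrawal harms captured, the same in both arms.

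- Scheduled: 12 × (0.30 + c × 0.10)
- As-needed: 12 × (0.10 + c × 0.30)

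| c | Scheduled | As-needed | Difference |
|---|---|---|---|
| 1.00 | 4.8 | 4.8 | 0.0 |
| 0.50 | 4.2 | 3.0 | 1.2 |
| 0.25 | 3.9 | 2.1 | 1.8 |
| 0 | 3.6 | 1.2 | 2.4 |

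The tilt disappears with full capture. It also depends on capture being equal across arms. If staff recorded every withdrawal harm in the as-needed arm and none in the scheduled arm, the counts would be 12 × 0.30 = 3.6 scheduled and 12 × (0.10 + 0.30) = 4.8 as-needed, which reverses it.

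**Step 4. What 12 per arm can show.** Zero events in 12 leaves a two-sided exact 95% upper limit of 1 − 0.025^(1/12) = 26.5%. For 10% vs 30% at two-sided 5%, the normal approximation with pooled variance gives z = (0.20 × √12 − 1.96 × √(2 × 0.2 × 0.8)) / √(0.09 + 0.21) = (0.693 − 1.109) / 0.548 = −0.76, a power of about 22%. No firm safety comparison is possible with or without the change.

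**The case against.** The strongest reply is that collection is not confined to the list. The adverse-event definition is broad, the list is introduced as what monitoring will include rather than what it is limited to, and the scales have mild and unrelated categories that would be little used if only serious or related events were recorded. This stands: the withdrawal harms are not excluded. The weakness is that they are not solicited.

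Second, under-treatment is partly measured elsewhere. The number of infants switched to the standard arm is a primary outcome in Section 3.0, and one stated trigger is a study-group infant receiving all eight possible doses in 24 hours (Section 7.0). Finnegan scores are collected, and readmission for withdrawal-related problems is sought at 4-8 weeks (Sections 8.0 and 15.0). This also stands and offsets part of the concern, but none of these records weight loss, gavage feeding or seizures as such.

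Third, the relatedness scale reserves its lowest category for events clearly not related, so a withdrawal complication in the as-needed arm might well be recorded as possibly related. That is fair, and it is why the direction in Step 3 is conditional. It does not restore consistency, because the judgement may still differ by arm.

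A reader might infer that the safety comparison is biased toward the as-needed arm by design. The documents do not support that. No between-arm safety comparison is planned, serious and related events are covered in both arms, and apnea, a harm of morphine, is also unnamed. Nor do the documents give any rate from which to say how many infants would go unrecorded.

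**Conclusion.** The point holds as a gap in how harms are collected, not as a bias in an analysis. Section 9.0 solicits one of the five harms it describes, and expected, non-serious withdrawal harms may be recorded inconsistently. If as-needed dosing does lower morphine exposure, and if capture of withdrawal harms is incomplete and similar in both arms, a descriptive table would look more favourable to the as-needed arm than it should. The size cannot be taken from the documents. Under the assumed rates above it is 1.2 to 2.4 expected events out of 12 per arm at 50% to 0% capture. The feasibility objectives are untouched. The change is still worth making because it is cheap and because the pilot is meant to inform a larger trial.

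A related inconsistency affects the same data. Section 9.0 first ends adverse-event recording at hospital discharge, and later continues tracking until the follow-up call at 4-8 weeks of age. Whether a withdrawal harm after discharge is recorded depends on which statement is followed.

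**What to change.** In Section 9.0, list all five harms as solicited events, each with a short definition: weight loss above the 10% threshold already stated, gavage feeding, seizure, depressed consciousness as already graded, and respiratory depression or apnea. Record presence or absence for every infant in both arms, regardless of relatedness or seriousness, and keep collecting after a switch to the standard regimen. Tabulate them descriptively by randomized arm, without tests. Reconcile the two end points for adverse-event recording so that one window applies throughout.

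The cost is about four extra REDCap fields (five harms less the one already named), some abstraction time and a longer adverse-event table. The scoring form already has a daily-weight entry and a convulsions item, and Section 9.0 says that infants on morphine have routine cardiopulmonary monitoring, so much of the source information should already exist. No treatment rule changes.
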